9.3.2 Serum immunoglobulin concentrations (IgA, IgE, IgM) at each scheduled assessment

Immunoglobulins (IgE, IgA and IgM) will no longer be summarized; IgE, IgA and IgM concentrations will be listed only.

9.4 Influence of Rozanolixizumab on vaccination titers

9.4.1 Vaccination titers against *Streptococcus pneumoniae*, *Neisseria meningitidis*, and *Haemophilus influenzae* in splenectomized study participants

Vaccine specific antibodies concentrations will be listed to capture absolute values in vaccination titers against *Streptococcus pneumoniae*, *Neisseria meningitidis*, and *Haemophilus influenzae* in splenectomized study participants by visit using the SS.

9.4.2 Percent change from Baseline in vaccination titers against tetanus in all study participants

Anti-tetanus toxoid serum titers will be listed to capture absolute values and the percent change from baseline in vaccination titers against tetanus in all study participants by visit using the SS.

10 SAFETY ANALYSES

All safety analyses will be presented using the SS. Listings will be presented by period, treatment group and participant; tabulations will be presented by period (treatment and safety FU Period) and treatment group.

Unless otherwise specified, safety analyses will be presented by safety treatment group as defined in Section 3.6.

For results disclosure on public registries (eg. Clinical Trials.gov), treatment-emergent adverse events and treatment-emergent serious adverse events will be published.

10.1 Extent of exposure

The following summary will be created using the SS by treatment group:

- a) Study IMP duration and Subject-Years of Time at Risk will be summarized using descriptive statistics.
 - The number of days on IMP (extent of exposure), will be summarized using descriptive statistics for the overall treatment period.

The number of days on IMP will be calculated as follows:

$$\text{Number of days on IMP} = [(\text{Date of Last Dose Received}) - (\text{Date of First Dose Received})] + 1$$

In all calculations, if a patient dies and the date of death is missing, the date of death can be imputed as the date of last infusion of the treatment the participant was taking.

- Subject-Years of Time at Risk:
 - o For study participants who complete the study as planned and continue into an open label study (and, therefore, do not have the SFU visit in the parent study)

$$\text{Date of last visit} - \text{Date of first dose} + 1$$

- o For study participants who die prior to the final visit

Date of death – Date of first dose + 1

- For all other study participants, use the minimum of the following:

Date of last dose – Date of first dose + 56

Date of last clinical contact – Date of first dose + 1

- This last group could include study participants who discontinue early, study participants who complete the study as scheduled but choose not to continue into an open label study, or study participants who are ongoing in the SFU period at the time of the data snapshot.
- The total time at risk is calculated as the sum of the person-time at risk (days) across all participants in the population divided by 365.25.

As described in the protocol, a fixed-unit doses across body weight tiers and treatment arms will be employed in this study according to the following scheme, as presented in [Table 10-1](#) below

Table 10-1: TP0003 dose levels and weight tiers of rozanolixizumab

Bodyweight	Starting dose	Maintenance dose level 1	Maintenance dose level 2	Maintenance dose level 3
>35 to <50kg				No weight adjustment █
≥50 to <70kg				
≥70 to <100kg				
≥100kg				

Note: the starting dose of █ is not applicable in Protocol Amendment 3, but is applicable in earlier protocol versions.

If a study participant is in the lowest body weight tier (below 50kg) and is on the lowest dose level with a platelet count between $\geq 150 \times 10^9/L$ and $< 400 \times 10^9/L$, the investigator might decide to temporarily stop treatment according to medical judgement based on the observation of platelet variability. If the platelet count increases above $400 \times 10^9/L$ then treatment must be stopped anyway.

The placebo arm will use 0.9% sodium chloride aqueous solution (physiological saline, preservative free) for sc administration, matching the volumes of the rozanolixizumab arm.

A listing with all drug administration details including date, start and stop time of infusion, interruptions, discontinuations, dose, volume delivered, percent of planned dose and reasons for any interruptions or discontinuations will be created using the SS.

10.2 Adverse events

10.2.1 Data considerations

Adverse events will be recorded from the time of informed consent until study completion. All AEs will be coded (Section 3.8).

In addition, AEs will be classified according to the Common Terminology Criteria for Adverse Events (CTCAE) Version 5 or later for severity. For any AEs where it is not possible to provide

a CTCAE grading, the events will be assessed using a standard intensity classification (mild, moderate and severe). For the purpose of the tabulations all CTCAE severity classifications will be mapped to a mild/moderate/severe grade as described below:

CTCAE Toxicity Grade: Severity

- Grade 1: Mild
- Grade 2: Moderate
- Grade 3, 4, 5: Severe
- Not gradable

In summaries including intensity, the categories will be summarized according to the following:

Grade: Intensity

- Grade 1: Mild
- Grade 2: Moderate
- Grade 3: Severe

For AEs that were not classified according to the CTCAE Toxicity (Severity) criteria, the standard intensity Grade will be applied. In case there are mismatches between Severity and Intensity Grade, the worst case (i.e., the most severe grade) will be applied.

Treatment-emergent AEs are defined as AEs starting after the time of first IMP administration up to and including 8 weeks (56 days) after the final dose.

AEs before first dosing and AEs after 8 (56 days) weeks following the final dose will be combined in one category and listed.

Where dates are missing or partially missing, AEs will be assumed to be treatment-emergent unless evidence exists that does not allow the AE to be treatment-emergent. Handling of missing dates for classification of AEs as TEAEs is described in Section 4.2.2 .

The following rules will be used to assign a TEAE to a study period:

TEAE-Treatment Period: a TEAE will be assigned to the Treatment Period for the tabulations if the start date of the event is on or after the date of the first administration of IMP on Day 1, up to 7 days following the final dose of IMP.

TEAE-Safety Follow up Period: a TEAE will be assigned to the Safety Follow up Period for the tabulations if the start date of the event is greater than 7 days after the date of the final dose of IMP until 8 weeks following the final dose; events starting later than 8 weeks following the final dose of IMP are not considered TEAEs.

In the case of early withdrawal in the Treatment Period, a TEAE will be assigned to the Treatment Period based on the last received infusion plus 7 days. Subsequent TEAEs (up to 8 weeks post-last dose) will be assigned to the Safety Follow up Period.

A TEAE will be counted as a TEAE related to IMP if the response to the question “Relationship to Study Medication” is “Related”.

AEs will be presented as “number of participants (percentage of participants) [number of events]”. In this style of output, “[number of events]” will include all cases of an AE including repeat occurrences in individual participants, while “number of participants” will count each participant only once. AE analysis will be summarized by Treatment and follow up periods.

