3.2.2 Study periods

The following study periods are defined for this trial:

- Prolonged Screening Period: splenectomized participants will be required to attend a Prolonged Period prior to the Screening Visit for the assessment of vaccination titers and to receive, if applicable, the required vaccinations, which will extend the total study duration by up to 20 weeks.
- Screening Period (up to 4 weeks): Starts at the time of the informed consent date and ends the day before the first dose administration of study drug (i.e. generally the day before Day 1 visit date).

Note: after signing the ICF splenectomized participants will go first through the Prolonged Screening Period and then to the Screening Period, while the non-splenectomized will go directly to the Screening Period.

- Dose Adaptation Period (12 weeks): Starts on the day of the first dose administration of study drug (Day 1) and ends after the Week 13 visit assessments.
- Maintenance Period (12 weeks): Starts on the day after the 12-week Dose Adaptation Period (Week 13) and ends after the Week 25 visit assessments (or at the Early Withdrawal (EW) Visit for study participants withdrawn from the study before Week 25 visit).
- Treatment Period: Starts on the day of the first dose administration of study drug (Day 1) and ends after the Week 25 visit assessments (or at the EW Visit for study participants withdrawn from the study before Week 25 visit). It is the combination of the Dose Adaptation Period and the Maintenance Period.
- Safety Follow-up Period (SFU): Starts with last dose administered and ends 8 weeks after final dose administered.

A study participant is considered to have completed the study if he/she has completed all phases of the study including the SFU Period or has successfully been enrolled (completed Visit 1 in TP0004) into TP0004 at Week 25.

A study participant will be said to have completed the SFU period if she/he had completed the last scheduled visit in the SFU period.

Study participants will have an EOS Visit performed 8 weeks after the final dose of IMP (unless they are enrolling in TP0004 at Week 25), or upon discontinuation of the study.

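### SAP 10.2.1 closes the TEAE Treatment Period 7 days after the final dose, which is half the bi-weekly dosing interval of the analysed participants, so completers' TEAEs starting on Days 163 to 169 are tabulated as Follow-up

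*SAP*

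**What the plan says.** SAP 3.2.2 defines the study periods. For the main treatment phase it gives this span: "Starts on the day of the first dose administration of study drug (Day 1) and ends after the Week 25 visit assessments". People who leave early have a different end point: "or at the EW Visit for study participants withdrawn from the study before Week 25 visit". The Safety Follow-up Period "Starts with last dose administered and ends 8 weeks after final dose administered".

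SAP 10.2.1 sets its own rule for placing TEAEs in periods. An event belongs to the Treatment Period if it starts "on or after the date of the first administration of IMP on Day 1, up to 7 days following the final dose of IMP". Later events, up to 8 weeks after the final dose, go to Safety Follow-up. For early withdrawals, "a TEAE will be assigned to the Treatment Period based on the last received infusion plus 7 days".

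The split reaches the output: under SAP 10, "tabulations will be presented by period (treatment and safety FU Period) and treatment group".

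The SAP Introduction and the notes in SAP 2.3 say that the study stopped after 33 participants had been randomized to bi-weekly dosing, that dosing was planned until Week 23, and that nobody received weekly dosing.

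**The concern.** The same period name covers two different intervals. For a bi-weekly completer, the AE tables close the Treatment Period a week before the SAP's general definition does. The SAP gives no reason for 7 days. That length would fit a weekly schedule, which nobody in this analysis followed.

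The rule also treats the last dose differently from every earlier one. An event starting 8 to 14 days after an earlier bi-weekly dose counts as Treatment. An event starting the same number of days after the final dose counts as Follow-up.

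Rollover participants show the effect most clearly. SAP 10.2.1 states that "Adverse events will be recorded from the time of informed consent until study completion", and SAP 3.2.2 counts a participant as complete who "has successfully been enrolled (completed Visit 1 in TP0004) into TP0004 at Week 25". If rollover happens on the day of the Week 25 visit, every TEAE labelled Follow-up started on or before the last treatment visit. A reader of the by-period tables would take those events as arising after treatment had ended.

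**Working it through.** **Inputs**
- Last planned dose: Week 23, bi-weekly (SAP 2.3, note on earlier protocol versions).
- Last Treatment Period visit: Week 25, Day 169 (SAP 3.2.2 and 2.3; Protocol Table 1-4).
- End of Safety Follow-up for bi-weekly participants: Day 211 (SAP 2.3, note).
- TEAE window: 56 days after the final dose (SAP 10.2.1).
- TEAE Treatment Period cut-off: final dose + 7 days (SAP 10.2.1).

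**Reproducing the plan's own figure**
- Day = 7 × (week − 1) + 1.
- Week 23: 7 × 22 + 1 = Day 155. Week 25: 7 × 24 + 1 = Day 169.
- 155 + 56 = Day 211, the stated end of Safety Follow-up. This confirms Day 155 as the nominal final dose.

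**The gap at nominal timing**
- Cut-off in 10.2.1: 155 + 7 = Day 162.
- End of Treatment Period in 3.2.2: Day 169.
- Difference: 169 − 162 = 7 days (Days 163 to 169), and 7/169 = 4.1% of planned treatment days.
- TEAE Follow-up without rollover: Days 163 to 211, or 211 − 163 + 1 = 49 days. Of these, 7 (7/49 = 14.3%) fall on or before Week 25.
- TEAE Follow-up with same-day rollover: Days 163 to 169, so all 7 days fall on or before Week 25.

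**Overlap inside 3.2.2**
- Safety Follow-up starts at Day 155 and Treatment ends at Day 169: 169 − 155 + 1 = 15 days lie in both periods.

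**Comparison with weekly dosing (nobody treated this way)**
- Last dose at Week 24: 7 × 23 + 1 = Day 162. 162 + 7 = Day 169, so the gap is 0.

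**Visit windows**
- Assume the ±2-day window of the current protocol also applied in earlier versions. If the final dose shifts by a days and the Week 25 visit by b days, the gap is (169 + b) − (155 + a + 7) = 7 + b − a.
- Over the range −2 to +2 for each, the gap runs from 3 days (a = +2, b = −2) to 11 days (a = −2, b = +2). It never closes.

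**With 14 days in place of 7**
- 155 + 14 = Day 169, so the nominal gap is 0. With the same windows the difference is b − a, between −4 and +4 days.

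**The case against.** The best defence is that 10.2.1 is explicit, specific to TEAEs and anchored on dosing, so a programmer has exactly one rule to follow. That is true, and the rule is unambiguous on its own. It does not explain why the window is half the dosing interval of the people analysed, or warn a table reader that the period label means something different from 3.2.2.

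A second objection limits the claim. A reader might infer that 3.2.2 places Days 163 to 169 squarely in Treatment and that 10.2.1 overrides it. The documents do not support this, because 3.2.2 also starts Safety Follow-up at the last dose and so puts those days in both periods. 10.2.1 breaks a tie that 3.2.2 leaves open, but breaks it at a point that does not suit bi-weekly dosing.

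A reader might also infer the intended boundary from SAP 6.5.1, since the amendment log says the medication rule was changed to agree with the treatment period definition. One of the limits in 6.5.1 is a redacted interval after the last dose, so that section cannot settle the question. Nor does the ECG note in SAP 13.4 show a general conflict with the AE tables: its treatment-emergent wording applies only to the PR and QRS criteria, and the ECG schedule of the earlier protocol versions is not available.

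Finally, it is tempting to tie the TEAE periods directly to the Week 25 or EW visit. That makes new problems. If the EW visit is 2 days after an infusion, an event on post-dose day 3 would become Follow-up. After a long hold with the last dose on Day 99, the 56-day window closes on Day 155 (99 + 56), before Week 25, and the Follow-up interval would have negative length. The dose anchor is worth keeping.

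**Conclusion.** The point holds as a minor one. The 7-day window does not fit the bi-weekly regimen, and the period definitions in 3.2.2 and 10.2.1 do not agree. At nominal timing, 7 days (Days 163 to 169) of completers' TEAE onsets are tabulated as Follow-up although they fall within one dosing interval of the last dose.

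This rests on completers who received the Week 23 dose on schedule. The ±2-day range assumes that the current visit window applied earlier. The remark that rollovers' Follow-up events all start by Week 25 applies only to same-day rollover: the Protocol Amendment 3 summary shows that earlier versions allowed a 1-week window.

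A reader might conclude that the safety results themselves are wrong. They are not. Days 163 to 169 lie within 56 days of the final dose, so treatment-emergent status and total TEAE counts do not change. Both arms follow the same rule, the AE listing shows days since the most recent dose, and no inferential analysis is planned. The figures above are days, not events: the documents do not give the numbers of events, completers or rollovers. That the 7 days came from the weekly schedule is plausible from the arithmetic but is not stated.

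**What to change.** - **SAP 10.2.1:** replace 7 days with 14 days (one bi-weekly dosing interval) in the Treatment Period rule, the Safety Follow-up rule and the early-withdrawal rule. Keep the dose anchor and the 56-day limit. At nominal timing, TEAE Follow-up without rollover then runs from Day 170 to Day 211 (42 days).
- **SAP 3.2.2:** start Safety Follow-up on the day after the Treatment Period ends, which removes the 15-day overlap.
- **SAP 10.2.1, one added sentence:** state that the TEAE periods are counted from the final dose and may differ from the visit-based periods in 3.2.2.

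The cost is wording in two sections and one date derivation, with no new data. The small downside is that visit windows or a withheld last dose can still leave the TEAE boundary a little away from the Week 25 or EW visit date. The added sentence covers this.

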10.2.2 Adverse Event Summaries

The number and percentage of participants who experience AEs will be summarized by treatment group. The following outputs will be created:

- (1) Incidence of TEAEs (defined as the number and percentage of participants with at least one TEAE (incidence proportion)) – Overview. The following categories will be included by treatment arm:
 - Any TEAEs
 - AESMs
 - AESIs
 - Serious TEAEs
 - TEAEs leading to Study Discontinuation
 - Permanent withdrawal from IMP due to TEAEs
 - Drug-related TEAEs
 - TEAEs with CTCAE Grade 3 and above [or rated as ‘severe’ for events with no CTCAE classification]
 - All Deaths (AEs leading to death)
 - All Deaths (TEAEs leading to death)
 - TEAEs leading to dose modification (defined as TEAEs with an action taken with study medication of “dose increased” or “dose decreased”)
 - TEAEs resulting in temporary treatment interruption

The following summaries will be created by SOC, HLT, and PT

- (2) Incidence of fatal TEAEs by relationship
- (3) Incidence of Serious TEAEs by Relationship
- (4) Incidence of TEAEs leading to permanent discontinuation of IMP
- (5) Incidence of Non-Serious TEAEs Above Reporting Threshold of 5% of participants by System Organ Class and Preferred Term
 - AESIs are Potential Hy’s Law, defined as $\geq 3 \times \text{ULN}$ ALT or AST with coexisting $\geq 2 \times \text{ULN}$ total bilirubin in the absence of $\geq 2 \times \text{ULN}$ ALP, with no alternative explanation for the biochemical abnormality.
 - AESMs are severe headache, severe GI disturbance (ie, diarrhea, abdominal pain, vomiting), opportunistic infections, arterial and venous thrombotic and thromboembolic events.
 - AESMs and AESIs will be identified based on the assessment by the Investigator as recorded in the CRF. An AE will be counted as an AESM if there is a ‘yes’ response to the question “Is this an event of Special Monitoring?” and not otherwise. An AE will be counted as an AESI if there is a ‘yes’ response to the question “Adverse Event of Special Interest?” and not otherwise.

Listing will be presented by treatment group, most recent dose and participant for all AEs. This will include the onset date/time and outcome date/time of the event (including relative days), the AE duration, days since first dose of IMP, days since most recent dose of IMP, most recent dose, pattern of event, severity/intensity, relationship, action taken

and outcome. In addition, the listing will flag AEs that led to discontinuation, TEAEs, serious adverse events (SAEs), AESMs, and AESIs.

AEs of Focus:

AEs of Focus (AEOF) will be defined using Version 3.0 or later of “Adverse Events of Focus for the Rozanolixizumab program”. In addition, worsening thrombocytopenia and haemorrhagic events will be included as AEOF as described in AEOF Version 1.4. The following AEs are defined in the rozanolixizumab program as AEs of focus (please see Section 13.1 for more details)

- Headaches
- Gastrointestinal Disturbances
- Hypersensitivity Reactions
- Anaphylactic Reactions
- Injection Site Reactions
- Infusion Reactions
- Opportunistic Infections
- Reductions in Albumin and Plasma Proteins
- Effects on the Kidney
- Drug Related Hepatic Disorders
- Thromboembolic Events
- Hemorrhagic Events
- Worsening of Thrombocytopenia

AEOFs will be listed only.

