8.3.7 Adverse events of special interest

An AE of special interest is any AE that a regulatory authority has mandated be reported on an expedited basis, regardless of the seriousness, expectedness, or relatedness of the AE to the administration of a UCB product/compound.

Potential Hy's Law, defined as $\geq 3 \times \text{ULN}$ ALT or AST with coexisting $\geq 2 \times \text{ULN}$ total bilirubin in the absence of $\geq 2 \times \text{ULN}$ ALP, with no alternative explanation for the biochemical abnormality, must ALWAYS be reported to UCB as an AE of special interest (ie, without waiting for any additional etiologic investigations to have been concluded). Follow-up information should then be reported if an alternative etiology is identified during investigation and monitoring of the participant.

See Appendix 6, Section 10.6 for further information on liver safety monitoring.

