8.3.8 Adverse events of special monitoring

For rozanolixizumab, AESM that require immediate reporting (within 24 hours regardless of seriousness) to UCB are:

- Severe headache
- Severe GI disorders (ie, diarrhea, abdominal pain, vomiting)
- Opportunistic infection
- Arterial and venous thrombotic and thromboembolic events

An AESM is not necessarily a serious adverse event unless one of the seriousness criteria defined in the Appendix 3 (Section 10.3) is met. All AESM will follow the SAE recording and reporting procedures as indicated in Appendix 3, Section 10.3.

In case of severe headache or serious headache (regardless of severity), the headache questionnaire (Appendix 20, Section 10.20) must be completed. The questionnaire should also be completed in case of moderate headache although moderate headache is not considered an AESM. Additional procedures for management of headaches are provided in Appendix 22, Section 10.22.

Procedures for the management of diarrhea are provided in Appendix 23, Section 10.23.

Although hypersensitivity reactions including infusion-related reactions and anaphylaxis are not classified as AESM, these AEs will be monitored by the investigators. If such an event is suspected it should be managed according the guidance provided in Appendix 24, Section 10.24. In case of suspected anaphylaxis, the Sampson's Criteria (Sampson et al, 2006) (Appendix 21, Section 10.21) should be completed. All hypersensitivity reactions will be recorded and reported as per the AE reporting procedure outlined in Appendix 3, Section 10.3.

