13 APPENDICES

13.1 AE of focus (AEOF) for the Rozimab Program

AEOF Version: 3.0 or later, Date: 13Dec2021 will be used in this SAP as described below. In addition, worsening thrombocytopenia and haemorrhagic events will be included as AEOF as described in AEOF Version 1.4:

ARTICLE I. MedDRA 22.0 and 22.1 and 23.0 and 23.1 AND 24.0

The purpose of this document is to detail the approach to identifying TEAEs meeting criteria for AEs of focus (AEOF) for the Rozanolixizumab (also called Rozimab) program

The document is organized by MedDRA version. At the time of writing this document, MedDRA version 22.0 was planned to be used for all indications under investigation (MG, ITP, CIDP, HV). As there is no change between 22.0 and 22.1 and 23.0 and 23.1 and 24.0 regarding terms used in below selection criteria, all below specified algorithms apply to these Meddra versions. If future studies are planned which use a different (more recent) version of MedDRA, this document will be updated.

The MedDRA SMQ files version 22.0, 22.1, 23.0 and 23.1 are attached in the original document.

MedDRA SMQ file 24.0:

SMQ_spreadsheet_24_0_English.xlsx

Following Events are Adverse Event of focus For Rozanolixizumab for all indications:

No	Event (also included in Title of TFL output)	Selection criteria	Purpose CSR/ SSD/ IB
1	Headache (Note: also included in AESM if severe)	TEAE with HLGT='Headaches'	CSR/ SSD/ IB
2	Gastrointestinal disturbances (Note: also included in AESM if severe)	TEAE with HLT='Gastrointestinal and abdominal pains (excl oral and throat)' or HLT='Gastrointestinal signs and symptoms NEC' or HLT='Nausea and vomiting symptoms' or HLT='Diarrhoea (excl infective)' or HLT='Gastritis (excl infective)'	CSR/ SSD/ IB
3	Hypersensitivity reactions	SMQ='Hypersensitivity'	CSR/ SSD/ IB
4	Anaphylactic reactions	SMQ='Anaphylactic reaction' and	CSR/ SSD/ IB

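### The AESM row of the adverse-event overview rests on an investigator tick alone, so an unticked event that meets the SAP's own AESM definition is missing from that row

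*SAP*

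**What the plan says.** SAP 10.2.2 gives the definitions first. "AESMs are severe headache, severe GI disturbance (ie, diarrhea, abdominal pain, vomiting), opportunistic infections, arterial and venous thrombotic and thromboembolic events". The one AESI is potential Hy's law: transaminase and bilirubin thresholds, no raised ALP, and a judgement that nothing else explains the abnormality.

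It then fixes how they are counted: "AESMs and AESIs will be identified based on the assessment by the Investigator as recorded in the CRF". An AESM needs a yes "response to the question “Is this an event of Special Monitoring?” and not otherwise", and an AESI needs a yes "response to the question “Adverse Event of Special Interest?” and not otherwise". Both are rows of the TEAE overview.

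Three other places bear on this:

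- SAP 13.1 notes against the coded-term groups for headache and for GI disturbances: "Note: also included in AESM if severe". It carries a similar note, without the severity condition, against opportunistic infections.
- SAP 10.2.1 derives severity: "In case there are mismatches between Severity and Intensity Grade, the worst case (i.e., the most severe grade) will be applied".
- Protocol 8.3.8 lists the "AESM that require immediate reporting (within 24 hours regardless of seriousness) to UCB are" four event groups. Protocol 8.3.7 says potential Hy's law "must ALWAYS be reported to UCB as an AE of special interest".

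Occurrence of AESM is listed as an other safety endpoint in Protocol section 3 and SAP 2.2.2.1.

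**The concern.** The SAP gives a definition of AESM and then a counting rule that does not consult it. The phrase excluding any other route rules out a derived flag, and I found no planned comparison of the tick with severity, coded term or laboratory value.

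Disagreement between tick and definition is foreseeable. The Protocol uses two meanings of severe. Appendix 3 grades general intensity by whether usual daily activity is prevented. Appendix 22 grades headache by CTCAE, where severe means pain that restricts self-care. SAP 10.2.1 expects the two gradings to differ and takes the worse one, but a grade raised that way does not alter the tick. The same headache can then be severe in the analysis data and not be an AESM.

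At stake is the count for a named safety endpoint. SAP 3.9 drops formal efficacy analysis, so descriptive tables are what the study will report. With arms this small, one missed tick can turn an observed event into none.

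**Working it through.** The documents give no figure to reproduce, so the check is mainly a comparison of texts.

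**1. Definition against counting rule, by AESM category.**

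| Category | What the definition needs | Rule already in the SAP | Does it feed the AESM row? |
|---|---|---|---|
| Severe headache | Coded term and severity | 13.1 item 1 with 10.2.1 severity | No |
| Severe GI event (diarrhea, abdominal pain, vomiting) | Coded term and severity | 13.1 item 2 with 10.2.1 severity; item 2 is wider, as it includes nausea and gastritis terms | No |
| Opportunistic infection | Event type | 13.1 item 8: automatic terms plus physician adjudication | No |
| Thrombotic or thromboembolic event | Event type | 13.1 item 13 (SMQ) | No |

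For the first three categories, 13.1 says the events are in AESM. Under 10.2.2 that is untrue of any unticked one. An opportunistic infection confirmed by the study and safety physicians under 13.1 still does not reach the AESM row without the tick.

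**2. Where an unticked event still appears.** The overview has rows for any TEAE, serious TEAEs and TEAEs of CTCAE Grade 3 or above, and none of these uses the tick. The listing of all AEs shows severity, and AEs of focus are listed from coded terms.

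**3. Limits of those other outputs.**

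- The Grade 3 row does not say what the event was. Its bracket admits a severe intensity rating only where no CTCAE classification exists. Read literally, a CTCAE Grade 2 headache rated severe misses that row, although 10.2.1 would make it severe.
- The tables by SOC and PT cover fatal, serious and discontinuation events, and non-serious events above 5% of participants. AEs of focus are listed only under 10.2.2, although 13.1 still describes a stand-alone table for opportunistic infections.

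**4. Size of one discordant case.** Inputs: 33 randomized (SAP 2.3) and 2:1 allocation (Protocol 4.1). Actual arm sizes are not given. If the split followed the ratio, 33 × 2/3 = 22 on rozanolixizumab and 33 × 1/3 = 11 on placebo.

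- One missed event on rozanolixizumab: 1/22 = 4.5%, reported as 0/22.
- One missed event on placebo: 1/11 = 9.1%, reported as 0/11.
- One non-serious event on rozanolixizumab that is the only one of its PT is 4.5% of its arm, or 1/33 = 3.0% overall. Both are below the 5% threshold, so it would have no named row in a PT table.
- Effect on the Any TEAEs row: none.

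**5. AESI.** The definition in 10.2.2 uses at-or-above thresholds (3×ULN for ALT or AST, 2×ULN for bilirubin) and requires the absence of an alternative explanation. The Hy's-law row of SAP Table 10-2 uses strictly-above thresholds and has no such judgement, so the two are different criteria. A transaminase at exactly 3×ULN meets the AESI threshold but none of the Table 10-2 rows. Bilirubin at exactly 2×ULN with a transaminase above 3×ULN misses the Hy's-law row but reaches the listing through the row set at 1.5×ULN. The marked-abnormality table in 13.2.2 starts higher still, at 5×ULN for transaminases and, with a normal Baseline, 3×ULN for bilirubin.

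**The case against.** The case for leaving the rule alone is substantial. Using the investigator's designation is explicit and prespecified, and SAP 10.2.1 treats relatedness in the same way. Severity is itself an investigator rating, so a derived flag also rests on CRF entries. AESMs follow SAE reporting procedures within 24 hours, and the Protocol provides for SAE reconciliation (8.4) and source data verification (10.1.6). Nothing in the documents shows that ticks are missed. AESM is an other safety endpoint in a study stopped at 33 participants.

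Two stronger readings are tempting, and the documents do not support either:

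- A reader might infer that an unticked event vanishes from the safety overview. It does not. It leaves the AESM or AESI row only, and would be absent from the whole overview only if no AE were recorded at all, which is not an effect of the counting rule. Possible Hy's-law cases must also be reported as SAEs (Protocol Appendix 2 and Appendix 6), which brings them into the Serious row, and SAP 10.5.1 lists laboratory hits whatever the tick.
- A reader might infer that a Table 10-2 Hy's-law hit beside an AESI count of zero is an error. It can be correct, because an established alternative cause takes the case outside the AESI definition.

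These points remove any claim of a hidden safety signal and any case for replacing the tick. They do not answer the narrower point: the AESM row can disagree with its own definition and with 13.1, and the SAP has no step that would detect this.

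**Conclusion.** The point holds as a cheap improvement to the SAP. For AESMs the counting rule contradicts 13.1 and ignores both the 10.2.1 severity and the adjudicated opportunistic infections, so it can undercount a named safety endpoint. The effect is confined to the AESM row.

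For AESIs the tick must stay, because the definition contains a clinical judgement that no laboratory rule can supply. What is missing there is a check that laboratory hits were considered.

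The number of discordant cases is unknown and may be zero. One case would be about 4.5% of the rozanolixizumab arm, on the assumed 22:11 split.

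**What to change.** In SAP 10.2.2, delete the words that exclude any other route and keep the CRF tick. Then add:

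- **AESM.** Derive a second flag from coded terms: the 13.1 headache group; diarrhea, abdominal pain and vomiting terms only, not the full 13.1 GI group; opportunistic infections as adjudicated under 13.1; and the thromboembolic SMQ. Use the 10.2.1 severity where the definition requires a severe event. Query mismatches between tick and flag before database lock. Count an event if it is ticked or meets the derived definition, and list the mismatches that remain.
- **AESI.** Apply the at-or-above thresholds of the AESI definition, not those of Table 10-2, to trigger review for an alternative explanation. List any laboratory hit that was not ticked. Do not count it automatically.

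The cost is a small amount of programming and a reconciliation round. Most of the rules are already specified in 10.2.1 and 13.1; the narrower GI term list is new. The documents do not say that any of it is already programmed. The AESM count can only rise, so the table footnote should state both sources.
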